4.2 Exclusion Criteria

We will exclude patients who meet any of the following criteria:

1. The hernia that the patient is being evaluated for has undergone prior repair (ipsilateral recurrent hernia)
2. Any contraindications to general anesthesia (including malignant hyperthermia)
3. Allergies to local anesthesia
4. Evidence of hernia incarceration or bowel strangulation
5. Active local or systemic infection that would preclude the use of mesh for hernia repair
6. Need for concurrent surgical procedure at the time of hernia repair
7. English is not the patient’s primary language
8. Enrollment in other research studies

Patients with dementia or other cognitive dysfunction will not be excluded as long as there is a caregiver available to participate in the consent and follow-up procedures.

Provide a statement that all candidates meeting any of the exclusion criteria at baseline will be excluded from study participation and then list each criterion.

List as many criteria as necessary to clearly define your study population.

- *Specify health status or any clinical conditions (e.g., life expectancy, co-existing disease) or other characteristics that precludes appropriate diagnosis, treatment or follow-up in the trial.*
- *Clinical/laboratory indicators of current status, obtained within XX days prior to randomization. List the specific tests to be performed and the narrowest acceptable range of laboratory values for exclusion, consistent with disease and/or safety. Include as many as necessary.*
- *Specify any exclusion related to pregnancy, lactation, or plans to become pregnant. Specify methods for assessing current status and willingness to use contraception, if applicable. Include as many as necessary.*

- *Use of [excluded drugs, behavioral interventions, devices, etc.] within XX days prior to study entry. Treatment with another investigational drug or intervention (with time frame).*
- *For drug studies: allergy/sensitivity to study drugs or their ingredients.*
- *Cancer*
- *Current drug or alcohol use or dependence that, in the opinion of the site investigator, would interfere with adherence to study requirements.*
- *Inability or unwillingness of individual or legal guardian/representative to give written informed consent.*

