9.2.1 Treatment Assignment Procedures

We will randomly assign older patients having inguinal hernia surgery to one of the two study arms: (1) local anesthesia or (2) general anesthesia. Our goal for enrollment will be a total of 80 participants with 40 participants in each arm and a total of 40 participants from each site. We will use a stratified randomization scheme with blocking within strata. Stratification factors include hospital location (Dallas or Houston) and age (65-75 or 75+ years). Equal allocation by strata will be used so that differences among hospitals and age groups will be balanced. Randomized assignments will be generated ahead of time for each combination of strata and placed within stored and numbered envelopes kept at each hospital location. We will generate 20% more assignments than necessary to allow for potential withdrawals. Before patients are enrolled, physicians, patients, and research coordinators will not know which anesthesia modality will be assigned. Once patients are enrolled, the next envelope that applies to that participant (based on stratification factors) will be selected and labeled with the date and time of enrollment, the patient’s name, and the research team member responsible for enrollment. The labeled and unopened envelope will be photographed for our records and the envelope number will be recorded in the participant’s record.

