9.2.2 Sample

There is no widely accepted method for estimating statistical power for a pilot study since, by definition, it is not powered to detect significant differences between groups. Instead, the goal is to demonstrate feasibility of conducting a fully powered trial and to provide some baseline information that can assist with estimation of the final sample size for the multisite trial. However, our sample size of 80 patients over 2 years (20 patients per site per year) does provide 80% power at $\alpha < 0.05$ for a 30 minute difference in operative and recovery time, assuming a common standard deviation of 45 minutes and a total operating + post-anesthesia unit time of 180 minutes for the general anesthesia group (consistent with our preliminary data). We would also have 80% power to detect a 5-point difference in quality of life on the Carolinas Comfort Scale, given prior published data on this instrument.^{20,21} Additionally, we generated 1000 bootstrap samples using data from our prior retrospective study comparing local versus general anesthesia for hernia repair. Each sample contained 40 patients who had surgery under local anesthesia and 40 under general anesthesia. We then evaluated the range of estimated mean and standard deviation for total operative and recovery time across all 1000 samples and found that the mean range (156-205 minutes) and standard deviation (42-113) provided reasonable and stable estimates for the actual values in the original sample. This provides further evidence that a sample size of 80 patients would provide reasonable data for estimating sample size for a fully powered multisite randomized trial.

Describe the treatment assignment procedures (randomization, minimization, relevant criteria, etc). If such procedures are proposed describe rationale as well as the procedure.

Plans for the maintenance of trial randomization codes and maintaining appropriate masking for the study should be discussed, including the timing and procedures for planned and unplanned breaking of randomization codes should be included. Include a statement regarding when unmasking may occur and who may unmask.

If the randomization will be stratified, indicate whether (and why) there is a sample size goal for each stratum. Identify what factors (if any) will be used to stratify the randomization.

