 - i. Confusion Assessment Method (CAM) short form: The CAM is the most widely used instrument for detection of delirium, with typical sensitivity of 94% and specificity of 89% across multiple studies.²⁶ The instrument is scored on a 7-point scale and we will consider a 0.5 standard deviation difference as the minimal clinically significant difference.²⁴ Items include evaluation of attention, disorganized thinking, and altered levels of consciousness.
 - ii. Montreal Cognitive Assessment (MoCA) 5-minute form: The MoCA is a widely used tool for detection of dementia and other cognitive impairment, and is sensitive when used as a global cognitive screening tool.²⁷ The 5-minute form was developed to (1) reduce the significant time burden of the longer version which typically takes 15 minutes to complete, while (2) maintaining the psychometric advantages of the longer form, and (3) facilitating assessment by

telephone rather than in-person interviews. The instrument evaluates memory/attention, language fluency, orientation, and recall. The 5-minute MoCA has strong correlation with the full version ($r=0.87$), maintains the discrimination of the full version (area under the curve 0.78 versus 0.75 for full version, $p>0.05$), and has strong test-retest validity (intraclass correlation coefficient 0.89).²⁷ Since the 5-minute MoCA was also developed for testing by phone or in person, it meshes with our protocol plans to conduct immediate and long-term follow up by phone. A difference of 3 points is typically considered clinically significant.²⁷

- iii. Trail Making Tests Parts A and B: The Trail Making Test is one of the most popular neuropsychological tests for detecting processing speed, attention, and visual scanning.²⁸ Part A requires participants to draw a line between circles containing numbers, and the circles must be connected in numerical order. Part B is similar, but alternates letters and numbers (1, A, 2, B, et). Both items are scored as time to completion and then normalized to population data based on age and education.²⁸ To address ceiling effects on Part B, we will use the efficiency score for individuals who do not complete the instrument in <300 seconds.²⁹ A 0.5 standard deviation difference in time is considered clinically significant.²⁸
 - b. Timing: All measures will be administered at baseline, prior to discharge, at 48 hours after discharge, at 2 weeks after surgery, and at 6 months after surgery
- 4) Outcome: Pain

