9.5.2 Analysis of secondary/clinical comes

For comparison of secondary/clinical outcomes we will use the Wilcoxon rank-sum test to compare continuous variables and the likelihood ratio chi-square to compare proportions of categorical variables. Our prior work suggests that there are no significant differences in effects by subgroups categorized by comorbidity or gender. Consequently, we do not plan any subgroup analysis.

Describe the descriptive and inferential statistical methods that will be used to analyze the outcomes and other study data. Specify any confounding variables for which it is anticipated adjustment will be made.

In accordance with NIH policy, unless data from prior studies strongly support no significant differences of clinical or public health importance in the intervention effect between gender and racial/ethnic subgroups, investigators should include a statement noting that a valid analysis of the intervention effect will be performed in these subgroups. If data from prior studies do not strongly support the existence of significant differences in the intervention effect between subgroups, then the analyses need not have high statistical power for detecting clinically meaningful differences.

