9.5.3 Missing data

A complete-case analysis will be performed for the primary analysis of survey and other data. To test sensitivity of the survey results to missing data, we will use multiple imputation with either Poisson or negative binomial regression (depending on overdispersion). For instruments scored by time to completion, we will employ multiple imputation with chained equations. Analysis will then proceed using post-imputation methods that take into account the variance of imputed values across samples (i.e. “pooling rules”).

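### Trail Making Part B puts completers on normed time and those who miss 300 seconds on an undefined efficiency score, so the slowest patients can be mis-ranked

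*Combined protocol and SAP*

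**What the plan says.** Section 9.4.2, item 3(a)(iii), sets the ordinary score for both parts of the test: "Both items are scored as time to completion and then normalized to population data based on age and education". For Part B it adds the exception: "To address ceiling effects on Part B, we will use the efficiency score for individuals who do not complete the instrument in <300 seconds". The clinical threshold is stated on the time scale only: "A 0.5 standard deviation difference in time is considered clinically significant". The efficiency score is adopted by citing an evaluation of it in veterans. Its formula, units and direction are not given, and the plan does not say whether it is normed.

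Three later uses take Trail Making as an ordinary score:
- Section 9.5.2, for the arm comparison: "we will use the Wilcoxon rank-sum test to compare continuous variables". It has no rule for people who do not finish.
- Section 9.5.1 enters a single Trail Making term in each redundancy regression.
- Section 9.4.1, outcome 7, takes means and standard deviations of continuous outcomes to size the next trial.

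Section 9.5.3 covers missing values: "For instruments scored by time to completion, we will employ multiple imputation with chained equations". It does not mention non-completers.

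On population and size, Section 4.2 states: "Patients with dementia or other cognitive dysfunction will not be excluded as long as there is a caregiver available". Section 9.2.1 states: "Our goal for enrollment will be a total of 80 participants with 40 participants in each arm". The schedule in Section 6.1 includes the test before discharge on the day of surgery.

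**The concern.** A completion time and an efficiency score are different measurements. On its face, more time is worse and more efficiency is better. A rank-sum test on a column holding both places each non-completer according to how the two scores happen to be coded, not according to how slow the patient was. The 0.5 SD threshold has no meaning for someone who has no time.

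The switch applies only to the slowest patients, in a trial that admits people with cognitive impairment and tests them hours after anesthesia. The trial's working hypothesis is better cognition after local anesthesia. If that is true, non-completion will be more frequent in the general arm, and the change of scale will be related to treatment.

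Trail Making is a secondary outcome, but its scores also feed two primary feasibility outcomes: the rule that drops an instrument when its adjusted R-squared exceeds 40%, and the estimates used to size the next trial and choose its primary outcome.

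**Working it through.** **1. Is there a figure to reproduce?** No. The plan states no power, SD or non-completion rate for Trail Making. Its power statement in Section 9.2.2 concerns minutes of operative and recovery time and has no bearing here.

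**2. The two scores side by side.**

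| | Finishes in under 300 s | Does not |
|---|---|---|
| Quantity | time | efficiency score |
| Normed for age and education | yes | not stated |
| Direction after scoring | not stated | not stated |
| 0.5 SD threshold applies | yes | no |

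**3. Where would non-completers land?** Assumptions, none from the documents: lognormal times with log-SD 0.5, a true 0.5 SD benefit of local anesthesia, 24 connections in Part B, 40 per arm. Entries are the mean rank position of non-completers (0 = best, 1 = worst) when 5% / 10% / 20% / 30% of the general arm do not finish.

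| Completers' score with efficiency coding | Position |
|---|---|
| (a) Seconds, or T-score with high = slow; efficiency 0 to 1 | 0.02 / 0.04 / 0.08 / 0.12 |
| (b) z-score with high = good; efficiency as connection count | 0.02 / 0.04 / 0.08 / 0.12 |
| (c) z-score with high = good; efficiency 0 to 1 | 0.21 / 0.15 / 0.13 / 0.15 |
| (d) z-score with high = slow; efficiency 0 to 1 | 0.77 / 0.66 / 0.52 / 0.44 |
| (e) T-score with high = good; efficiency 0 to 1 | 0.99 / 0.97 / 0.93 / 0.89 |

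Only (e) places them correctly, and it does so by accident of units. Rank-sum power under (a) is 36% / 21% / 6% / 1%, against about 57% with correct ranking.

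**4. How large might the effect be?** A second model, also assumed: raw seconds, log-SD 0.5, general arm 30% slower, and non-completers scored as connections per second. For example, 12 connections in 300 s gives 12/300 = 0.04, which ranks ahead of any completer's time.

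Non-completion is 1 − Φ(ln(300/median)/0.5):
- Medians 80/104 s: 1 − Φ(2.64) = 0.4% and 1 − Φ(2.12) = 1.7%. With 40 per arm that is 0.2 and 0.7 patients.
- Medians 150/195 s: 1 − Φ(1.39) = 8% and 1 − Φ(0.86) = 19%, or about 3 and 8 patients.

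On one scale, the chance that a general-arm patient is slower than a local-arm patient is Φ(ln 1.3/(0.5√2)) = Φ(0.371) = 0.645 in both cases.

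On the mixed scale that chance is the sum of three parts: both finish and the general patient is slower; only the general patient finishes; neither finishes and the general patient was the faster.
- 80/104 s: 0.628 + 0.004 + 0.000 = 0.63. Simulated power is about 53%, against about 61% on one scale.
- 150/195 s: 0.457 + 0.067 + 0.007 = 0.53. Simulated power is about 8%, against about 61%.

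**5. Does the remedy work?** In the model of step 3, worst ranks for non-completers, or the efficiency score for everyone, gives power of 57% to 59% at general-arm non-completion of 5% to 40%. The full uncensored times give the same. Dropping non-completers gives 46% at 10% and 36% at 20%.

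**The case against.** The strongest reply has five parts.

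- **The efficiency score is defined in the cited paper.** That paper may give a direction and a relation to completion time. This stands as a limit on the point: the documents alone do not show which way the score runs. It does not remove the gap, because the plan itself states no mapping to normed time.
- **Large effects need many non-completers.** Table 3 in Section 9.4.2 allows 2 minutes for both trails together, so a Part B median of 150 s or more exceeds the protocol's own figure. This stands. With medians that fit Table 3, fewer than one patient per arm is expected not to finish and the loss is modest. Table 3 may be optimistic for older or impaired patients after anesthesia, but the documents do not show that.
- **The plan specifies normed scores, and step 4 uses raw seconds.** This stands, and step 4 is an illustration only. Step 3 includes normed codings and shows that the result depends on which is used.
- **Pooling is not stated outright.** True, but no separate analysis is planned and the regressions carry one Trail Making term. As for imputation, a patient with an efficiency score is not missing, so Section 9.5.3 does not say that such patients would be imputed as times.
- **Clinical comparisons are exploratory.** This stands, and it limits the severity.

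A reader might infer that non-completers will rank as best, or that the arm difference will shrink to nothing or reverse. The documents do not support either as a forecast. Each needs a particular coding together with a non-completion rate that the plan does not give.

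**Conclusion.** The point holds in a limited form. As written, Part B would combine normed time for completers with an unmapped efficiency score for those who miss 300 seconds. The most impaired patients could then be mis-ranked, and the 0.5 SD threshold does not cover them. Only the possibility of mis-ranking is established; its direction depends on coding that the plan leaves open.

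Under the assumed raw-seconds model, the cost in power runs from about 61% to 53% at medians compatible with Table 3, and from about 61% to 8% if 8% and 19% of the arms do not finish. The distortion of the pilot SD and of the redundancy R-squared follows from mixing units but has not been quantified. Severity is minor to moderate: this is one exploratory instrument, though its scores also inform the redundancy and sample-size outcomes.

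**What to change.** In Section 9.4.2, item 3(a)(iii):

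1. State the efficiency score's formula, range and direction.
2. For the rank-sum comparison, rank every Part B non-completer worse than every completer, ordered among themselves by efficiency score.
3. Report the proportion not finishing by 300 seconds, by arm and visit.
4. Wherever a mean, SD or regression term is needed, use one metric for all participants at all visits, for example the efficiency score for everyone, and restate the 0.5 SD threshold on that metric.

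The cost is a few sentences, settled before any unblinded analysis. No extra visits or tests are needed. Using the efficiency score for everyone means computing it for completers too. The downside is that non-completers have no normed time value, so under worst-rank scoring their order among themselves reflects efficiency and not the age and education norms.
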